	
A new e-diary or paper diary card to record solicited and unsolicited AE from Second Injection will be provided at Second Injection Visit- Day 56. The data in the completed e-diary or diary card provided during the Day-56 visit will be reviewed and data will be collected at visit on Day 84. Further details are outlined in Section 3.7 and 5.1.
 
All participants will be contacted on a weekly basis to be reminded to report any signs or symptoms of illness to study staff. Participants will either be contacted by the site weekly, or they will receive an automated message (email) with a link to answer questions about whether or not they had an SAE, an MAE or COVID-19 symptoms. Participants will also be asked on their day 7 contact about any events that might meet a pause or early termination criterion. The reporting and monitoring of any participant illness are consistent with meeting the primary efficacy objective. If a participant becomes ill, they will be asked to immediately proceed to the site designated by their local study team where they will be assessed and treated as deemed appropriate. Participants will also receive a telephone call every 4 weeks, to evaluate for the incidence of any SAE or MAE.
 
A subset of 50 participants will have additional immunologic testing performed, following the same visit schedule, to evaluate T-cell response to the Ad5-nCoV vaccine.
 
If a participant demonstrates signs or symptoms of illness, an unplanned in-person visit may occur for evaluation and possible treatment. If, for any reason following an electronic participant contact, the investigator would like to conduct an in-person visit (at home or at the site) with a participant, they may do so at their discretion.

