#### 3.2 Study Groups

A total of 500 participants will be enrolled to receive the vaccine. All participants will be monitored for solicited adverse events for 7 days, unsolicited adverse events for 28 days, SAEs and MAEs for the one year duration of the study, and antibody measurements at baseline, Day 28, Day 84, week 24, and week 52. A subset of 50 participants will have cellular immunity measured at those same intervals.

This protocol amendment provides for unblinding of participants who were entered into the study in the double-blind schedule. For participants who entered the double-blind schedule, the visit process will be as follows:

a) Sites will receive an unblinding list detailing participants who received placebo or study vaccine. Participants who received placebo will be invited to continue in the study under the

open-label study scheme and should make visits from V1.B (first vaccine) onwards, after signing the informed consent, completing visits on day 28 (V2.B), day 56 (second dose) (V3.B), day 84 (V4.B), week 24 (V5.B) and week 52 (V6.B). In this group of participants already enrolled, no antibody dosage collection will be performed at the V1B visit; the V1 values at study entry will be taken. The letter B is added to the visits to differentiate this group of participants who must reorganize the schedule of visits from the administration of the first dose of CoVID vaccine after the unblinding. The procedures for this group are detailed in Table 2.

b) Participants who, after the unblinding, are found to have received study vaccine at the initial visit, will complete the visits established by protocol together with the administration of dose 2 of the study (day 56) onwards, after signing the informed consent. In this group of participants there will be no changes in the nomenclature of the visits.

For both arms (placebo and study vaccine), efficacy contacts are restarted with the second injection visit.

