**Detailed description of study procedures and interventions is outlined in Section 5.1**

**Table 2. Procedures for the group of participants assigned to placebo arm. In-person visit**

	Visit 1.B	Visit 2.B	Visit 3.B	Visit 4.B	Visit 5.B	Visit 6.B
Intervention	Day 0 (First Injection)	Day 28	Day 56 (Seco nd Inject ion)	Day 84	Week 24	Week 52
Visit window		+/- 7 days	+/- 7 days	+/- 7 days	+/-14 days	+/-14 days
Informed Consent						
Review Consent		•	•	•	•	•
Collect Demographic and Participant Contact Information						
Blood sample collected for HIV viral load and CD4/CD8 counts					•	•
Urine Pregnancy test- women of childbearing potential	•		•			
Review Inclusion and Exclusion criteria [2]			•			
Medical History	•		•			
Check and record prior concomitant medication and vaccines	•		•			
Check and record intercurrent medical conditions	•		•			
Check Contraindications to vaccine	•		•			

Pre-injection vital signs	●		●					
Study group and treatment number allocation								
Screening conclusion								
Administration of Study Product	●		●					
Safety participant contact (Phone call or in-person visit)				Every 4 weeks (Day 28, 56 and 84 is in person)				
Efficacy participant contact (message) (a)				Weekly from Day 7- week 52 (visit window: +3 days)				
Safety participant contact: in-person visit	●	●	●	●	●	●	●	
Paper diary card or e-diary provided to participant	●		●					
E-diary or diary card reviewed with participant and data collected and uploaded to eCRF		●		●				
Immunogenicity participant contact: in-person visit		●	●		●		●	
Blood Sample Collected for ELISA and neutralizing Antibody testing (~25mL)		●		●	●		●	
Blood Sample Collection for ICS testing (~30mL) (b)		●		●	●		●	
Study conclusion							●	

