### 3.5 Efficacy participant contacts

Efficacy participant contacts will occur for all participants on a weekly basis. Email or text messages will remind participants to report any signs or symptoms of infection to the study staff. These participant contacts can also be in-person, by phone, via the Internet or any other suitable method. Each contact needs to be recorded in the study electronic case report form.

Any reported COVID-19 relevant symptoms (e.g. fever, cough, shortness of breath, etc. as per WHO case definitions - see below) will trigger laboratory testing for SARS-CoV-2 infection. The SARS-CoV-2 nucleic acid test is performed with a throat or nasal swab and repeated within 3 days later if the result is negative. PCR SARS-CoV-2 tests will be done at Laboratorios CMH/Argenomics. Every effort will be made to verify positive PCR tests in a national or regional reference laboratory. Participants with a positive nasal/throat PCR will have it repeated at the local laboratory every two days in the first week (up to a maximum of 3 PCRs) and then weekly until negative. A serum specimen will be collected at the time of illness presentation and be repeated between 3 and 4 weeks later for SARS-CoV-2 anti-N IgG antibodies to be performed at Nexelis Laboratories for all subjects presented with suspected COVID-19 symptoms, regardless of the result of PCR SARS-CoV-2 test.

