Participants will be provided with access to an e-diary or a paper diary card and a thermometer, and instructions about how to use them. The use of an e-diary instead of a paper diary card is dependent on the study site. Participants will be asked to record solicited AE for 7 days after receiving the vaccination, and unsolicited AE for 28 days, in their diary. The completed e-diary and diary cards will be reviewed, and data collected at the 28-Day safety in-person visit. A new diary will be provided at Day 56 and collected at Day 84. Non completion of the e-diary or diary cards will be investigated with the participant through telephone call(s) or any other convenient procedure. All data collected from the e-diary and diary cards will be uploaded into the eCRF.

- **Efficacy participant contacts**

All participants will have efficacy participant contacts weekly for 52 weeks following vaccination. There will be approximately 52 electronic efficacy participant contacts. All efficacy participant contacts will be text messages, although other electronic method such as by phone, e-mail, the Internet is suitable, if preferred. Each participant contact needs to be recorded in the study electronic case report form. The purpose of these participant contacts is to serve as a reminder to participants to report any symptoms of illness they may be experiencing, regardless of severity. Any possible COVID-19 relevant symptoms (e.g., fever, cough, shortness of breath, etc., according to WHO case definitions; see Section 3.8) will trigger laboratory testing for SARS-CoV-2 infection.

- **Illness participant contact visits (Confirmed or suspected infection during study)**

Participants will be provided detailed instructions regarding the signs and symptoms of COVID-19 disease at each participant contact and will be instructed to seek medical attention and notify study staff should symptoms occur filling the illness visit form and completing the eCRF. The form should be updated and sent and sent when the case meets the definition of severe COVID, and when the case resolves. Symptoms of concern include cough, fever, diarrhea, prolonged fatigue, respiratory symptoms, pneumonia, difficulty swallowing, loss of sense of smell and neurological events. For symptoms of interest, please refer to 3.8 efficacy participant contact.

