### 9.3.5 Analysis of exploratory endpoints

#### Exploratory endpoints

- Efficacy of two doses of Ad5-nCoV in preventing symptomatic disease of COVID-19 (confirmed by PCR) occurring 14 and 28 days to 52 weeks after vaccination, regardless of severity.
- Efficacy of two doses of Ad5-nCoV in preventing virologically (PCR) or serologically (four-fold increase in SARS-CoV-2 anti-N IgG from pre-immunization to post symptom, defined as Day 21-28 post illness blood test, or pre-symptom to post-symptom blood test) confirmed COVID-19 disease occurring 14 and 28 days to 52 weeks after vaccination, regardless of severity.
- Efficacy of two doses of Ad5-nCoV in preventing severe COVID-19 disease caused by SARS-CoV-2 infection from 14 and 28 days to 24 and 52 weeks after vaccination.
- Efficacy of two doses of Ad5-nCoV in preventing asymptomatic disease of COVID-19 (confirmed by N IgG antibody on week 52 after vaccination).
- Severity of COVID-19 cases among vaccine recipients (based on WHO or FDA criteria) as compared to the control group, to measure antibody-mediated disease enhancement (ADE).
- SARS-CoV-2 virus shedding in COVID-19 cases that occurred 28 days to 52 weeks after vaccination (detection of viral nucleic acid every 2 days after being confirmed).
- Genotype of SARS-CoV-2 virus isolates of COVID-19 cases that occurred 28 days to 52 weeks after vaccination.
- Suspected but unconfirmed cases of COVID-19 (either because of negative or no tests).
- Evaluate incidence of suspected but unconfirmed cases of COVID-19 (either because of negative or no tests).

Analysis of endpoints will be descriptive. PCR confirmed positive subjects will be classified as having severe or non-severe disease. Severity of disease, SARS-CoV-2 virus shedding and Genotypes SARS-CoV-2 virus isolates will be listed by subject and date, along with demographic data, including the study centre. Suspected but unconfirmed cases and asymptomatic cases will also be listed.

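### Section 3.2 restarts efficacy contacts at the second injection, contradicting the weekly contacts from Day 7 in Table 2, the schedule it names for former placebo recipients

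*Protocol*

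**What the plan says.** Section 3.2 sets out how participants from the former double-blind schedule continue in the open-label study. Those who had placebo receive their first Ad5-nCoV dose at V1.B and carry on by "completing visits on day 28 (V2.B), day 56 (second dose) (V3.B), day 84 (V4.B), week 24 (V5.B) and week 52 (V6.B"). For their procedures the section refers to a table: "The procedures for this group are detailed in Table 2". It then closes with a rule covering both former arms: "For both arms (placebo and study vaccine), efficacy contacts are restarted with the second injection visit".

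Table 2 takes V1.B as Day 0. Its row for efficacy contacts reads "Weekly from Day 7- week 52 (visit window: +3 days").

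The general sections agree with Table 2. Section 3.5 states: "Efficacy participant contacts will occur for all participants on a weekly basis". Section 5.1 states: "All participants will have efficacy participant contacts weekly for 52 weeks following vaccination". Section 3.3 also has all participants contacted weekly. None of these makes an exception for participants from the double-blind schedule.

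Two other provisions depend on these contacts. The exploratory endpoints in Section 9.3.5 count COVID-19 cases "occurring 14 and 28 days to 52 weeks after vaccination, regardless of severity". The Visit plan in the synopsis gives the first contact a safety function: "Participants will also be asked on their day 7 contact about any events that might meet a pause or early termination criterion".

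**The concern.** For a former placebo recipient, the second injection visit is V3.B, at Day 56 after the first active dose. Section 3.2 therefore places the restart of weekly contacts eight weeks later than a schedule that begins at V1.B, whereas Table 2 begins one week after V1.B. Both instructions apply to the same people, and Section 3.2 cites the table that it contradicts.

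Two things are at stake. The first is case ascertainment. Reported symptoms trigger the swab and the acute serum sample, and the weekly message is the scheduled prompt for reporting them. If some sites follow Section 3.2 and others follow Table 2, or if newly enrolled participants are prompted from Day 7 and former placebo recipients are not, early cases after dose 1 would be sought with unequal intensity. A swab or acute sample missed at the time of illness cannot be collected later.

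The second is early safety information. The suspension rule in Section 11.1 concerns Grade 3 events that begin on the day of injection or the two days after it. The Day 7 contact is the first scheduled query about such events, and the diary is not reviewed with staff until Day 28.

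**Working it through.** **Inputs**

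- Second injection for former placebo recipients: Day 56 (V3.B), window ±7 days (Section 3.2; Table 2).
- Message days listed in Section 3.5 before Day 56: 7, 14, 21, 35, 42 and 49. Day 28 is an in-person visit.
- Case windows: from 14 or 28 days to 52 weeks (Day 364) after vaccination (Sections 2.2.4 and 9.3.5). The dose that starts the clock is not stated.

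**Delay under Section 3.2.** 56 / 7 = 8 weeks from V1.B to the restart. With the visit window it is 49 / 7 = 7 to 63 / 7 = 9 weeks.

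**Contacts at stake**

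| Reading followed | Message contacts between V1.B and V3.B |
|---|---|
| Table 2, Sections 3.3, 3.5 and 5.1 | 6 (Days 7, 14, 21, 35, 42, 49), plus the Day 28 visit |
| Section 3.2 taken literally | 0, plus the Day 28 visit |

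The difference is six message contacts. It is five if V3.B takes place on Day 49, the early edge of its window.

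**What remains under Section 3.2.** The Day 28 visit takes place on either reading. The diary issued at V1.B covers 28 days, and the next is issued at Day 56. Table 2 spaces safety contacts every four weeks, and Section 5.1 starts the telephone calls at Week 8, so no further scheduled safety contact falls between Day 28 and Day 56. In that interval only participant-initiated reporting is left.

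**Share of the case window without weekly prompts.** The formula is (Day of V3.B − window start) / (364 − window start), if the window runs from dose 1.

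| Window start | V3.B on Day 49 | V3.B on Day 56 | V3.B on Day 63 |
|---|---|---|---|
| Day 14 | 35 / 350 = 10.0% | 42 / 350 = 12.0% | 49 / 350 = 14.0% |
| Day 28 | 21 / 336 = 6.25% | 28 / 336 = 8.3% | 35 / 336 = 10.4% |

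If the window runs from dose 2, contacts have already restarted when it opens and the share is 0%. At the nominal visit day the range is therefore 0 to 12.0% for the 14-day start and 0 to 8.3% for the 28-day start.

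**Size of the subgroup.** Section 1.3 gives a 2:1 ratio for the blinded design. Read as two vaccine to one placebo, about 1 / (2 + 1) = one third of those enrolled under it had placebo. The protocol does not say how many that was, and placebo recipients are only invited to continue, so no share of the 500 can be calculated.

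**The case against.** The strongest reply is that Section 3.2 itself designates Table 2 for this group, and that Table 2 and three further sections all require weekly contacts. A site would have to put one sentence above all of them before any contact was lost. Restarting could also mean resetting the contact count while contacts go on, and no sentence says that contacts stop. This stands in part. It shows that a gap is possible, not that one will occur. It does not remove the contradiction: the text gives no hint of a mere reset, and it labels Day 56 as the second dose, so the literal reading is the later restart.

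A reader might infer that former placebo recipients go unsurveilled for eight weeks. The documents do not support that. The Day 28 visit, the diary to Day 28 and self-reporting remain, and participants are told to contact the study team if symptoms develop. A reader might also count seven lost contacts between Day 7 and Day 49, but Day 28 is an in-person visit on either reading. Nor does the start of every case window necessarily lose its prompts: that requires the window to run from dose 1, and the principal efficacy objectives concern two doses.

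On safety, the Day 7 query appears only in the synopsis. Solicited events are recorded daily to Day 7, participants can telephone at any hour about medically attended or serious events, and serious events are reported within 24 hours. The loss is one scheduled early query, not early safety monitoring as a whole.

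Finally, no efficacy hypothesis is tested and cases are only listed and described, so no power or error rate is affected. That limits the consequence, although a listing still depends on how cases were sought.

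**Conclusion.** The contradiction is real and should be corrected. Section 3.2 conflicts with Table 2 for the same participants and with the weekly contacts for all participants in Sections 3.3, 3.5 and 5.1. Where a site follows Section 3.2 literally, a former placebo recipient misses six message contacts after the first active dose (five if V3.B falls on Day 49), including the Day 7 pause-rule query.

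At the nominal Day 56, the part of the case window without weekly prompts is 0 to 12.0% or 0 to 8.3%; the upper ends assume the clock starts at dose 1 and the zeros assume dose 2. For participants who had already received vaccine, the same sentence leaves it unclear whether contacts continue up to dose 2. The length of any gap for them cannot be worked out from the protocol.

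The harm is possible uneven ascertainment of early cases in one subgroup of unstated size, and one lost safety query. An actual undercount is not shown: the protocol gives no basis for estimating how many cases only the weekly prompts would find.

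**What to change.** Reconcile the closing sentence of Section 3.2 with Table 2: for former placebo recipients, weekly efficacy contacts run from V1.B, with the first on Day 7; for participants already vaccinated under the blinded schedule, they continue without a gap through the second injection. In Sections 2.2.4 and 9.3.5, state which dose starts the 14-day and 28-day windows.

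The cost is one amended sentence and one added definition. Table 2 already schedules the contacts and the protocol allows them to be automated messages, so no visit or sample is added. If sites have already worked to Section 3.2, record for each participant the date from which weekly contacts ran, so that the case listings can show who was not being prompted and when.

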### **3.3 Sampling/Study Schedule**

All participants will have at least six planned in-person visits on First Injection Visit and Day 28, Day 56 (Second Injection Visit), Day 84, Week 24, and Week 52. The first visit, the Screening visit, will entail reviewing the ICF, completing a medical history of the participant, reviewing inclusion and exclusion criteria, collecting samples, performing HIV viral load and CD4/CD8 counts. At that visit (First Injection Visit), a urine pregnancy test in women of child-bearing potential will be performed (local site or laboratory) . The pre-vaccination blood drawn will be performed at First Injection Visit to obtain a viral load and a baseline CD4 count (CMH laboratory), a baseline SARS-CoV-19 antibody (Nexelis Laboratories), and baseline immunogenicity levels. Participants are required to remain at the study site for a minimum of 15 minutes after receiving the vaccine to monitor for any vaccine-related AE.

Participants will be given access to an e-diary or paper diary card to record solicited AE from First Injection Visit- day 7 and unsolicited AE from First Injection Visit-28. Participants will review their e-diary or diary card with study staff at their second in-person visit on Day 28. A new e-diary or paper diary card to record solicited and unsolicited AEs from Second Injection will be provided at Second Injection Visit- Day 56. The data in the completed e-diary or diary card will be reviewed and data will be collected at visit on Day 84.

Data collected from e-diaries and diary cards will be uploaded into the participant's eCRF. Further details are outlined in Section 3.7 and 5.1.

All participants will be contacted on a weekly basis by the site (or through an automated message (email) with a link to answer the questions on whether or not they had SAE, MAE or COVID-19 symptoms) to be reminded to report any signs or symptoms of illness to study staff. The

reporting and monitoring of any participant illness are consistent with meeting the primary efficacy objective. If a participant becomes ill, they will be asked to immediately proceed to the site designated by their local study team where they will be assessed and treated as deemed appropriate. Participants will also receive a telephone call every 4 weeks to evaluate for the incidence of any SAE and MAE.

In-person visits on Screening visit and First Injection Visit, Day 28, Day 84, Week 24 and Week 52 will also be used for blood sample collection to assess for detailed immunogenicity response. Further details are outlined in Section 3.8 and 3.9.

A subset of approximately 50 participants will have additional immunologic testing performed, following the same visit schedule, to evaluate T-cell response to the Ad5-nCoV vaccine.

*If a participant demonstrates signs or symptoms of illness, an unplanned in-person visit may occur for evaluation and possible treatment. If, for any reason following a participant contact, the investigator would like to conduct an in-person visit with a participant, they may do so at their discretion.*

### 3.4 Procedures

Table 1. In-Person Visits

Intervention		Visit 1	Visit 2	Visit 3	Visit 4	Visit 5	Visit 6
		Day 0 (Screening and First Injection Visit)	Day 28	Day 56 (Second Injection Visit)	Day 84	Week 24	Week 52
Visit window			+/- 7 days	+/- 7 days	+/- 7 days	+/- 14 days	+/- 14 days
Informed Consent		•					
Review Consent		•	•	•	•	•	•
Collect Demographic and Participant Contact Information		•					
Blood sample collected for HIV viral load and CD4/CD8 counts		•				•	•
Urine Pregnancy test- women of childbearing potential		•		•			
Review Inclusion and Exclusion criteria		•		•			

Medical History	●		●				
Check and record prior concomitant medication and vaccines	●		●				
Check and record intercurrent medical conditions	●		●				
Check Contraindications to vaccine	●		●				
Pre-injection vital signs	●		●				
Study group and treatment number allocation	●						
Screening conclusion	●						
Administration of Study Product	●		●				
Safety participant contact (Phone call or in-person visit)			Every 4 weeks (Day 28, 56 and 84 is in person)				
Efficacy participant contact (message) (a)			Weekly from Day 7- week 52 (visit window: +3 days)				
Safety participant contact: in-person visit	●	●	●	●	●	●	●
Paper diary provided to participant	●		●				
E-diary or diary card reviewed with participant and data collected and uploaded to eCRF		●					
Immunogenicity participant contact: in-person visit	●	●	●		●	●	
Blood Sample Collected for ELISA and neutralizing Antibody testing (~25mL)	●	●		●	●	●	
Blood Sample Collection for ICS testing (~30mL) (b)	●	●		●	●	●	
Study conclusion							●

● is used to indicate a study procedure.

(a): If it is preferable, a phone-call or text instead of email for an efficient participant contact is acceptable

(b): In the subset of approximately 50 participants who will have cellular immunity measured

